## **12) Potential Benefits to the Subject**

The potential benefits of the Pure-Vu System include improved visualization of the bowel mucosa that is obscured due to inadequate preparation or residual fecal matter. Additionally, there is a potential reduced need for repeated colonoscopies due to insufficient colon preparation, these consequently may reduce pain, discomfort, risks, costs and lost productivity.

## **13) Study Purpose**

The aim of this study is to demonstrate that the use of the Pure-Vu EVS System can salvage inadequately prepared optical colonoscopies (OCs) to adequate OCs.

Inadequate OCs defined as such if any of the following are met:

- Boston Bowel Preparation Score (BBPS) < 6  
(Adequacy is defined as BBPS of 2 or greater in each segment)
- Inability to identify >5mm polyps

## **14) Primary Objective**

The primary objective of this study is to demonstrate the reduction of inadequate colonoscopies when Pure-Vu EVS System is used to salvage inadequately prepped colons.

## **15) Secondary Objectives**

The secondary objective of this study is to assess the impact of the Pure-Vu EVS System on patient outcomes.

## **16) Primary Endpoint**

Rate of incomplete colonoscopies due to inadequate preparation salvaged to adequate colonoscopies with the use of the Pure-Vu EVS System.

Inadequate OCs defined as such if any of the following are met:

- BBPS < 6 (Adequacy is defined as BBPS of 2 or greater in each segment)
- Inability to identify > 5mm polyps

Document Title: Colonoscopy: Demonstrating Effective Salvage of Inadequate Colonoscopies Utilizing the Pure-Vu EVS System	Outpatient	Document No. CL00052	Amendment 2.0	Page 22 of 46
---	------------	--------------------------------	-------------------------	---------------

## 17) Secondary Endpoints

The following secondary endpoints will be assessed:

1. Number of polyps and adenomas: type, location, size, pathology, and morphology, as well as:
  - Polyp Detection Rate (PDR)
  - Polyp Miss Rate (PMR)
  - Adenoma Detection Rate (ADR)
  - Adenoma Miss Rate (AMR)
  - Adenoma Per Colonoscopy (APC)
  - Adenomas Per Positive Patient (APP)
  - Sessile Serrated Adenoma Detection Rate
2. Boston Bowel Preparation Score (BBPS) before and after Pure-Vu EVS use
3. Other Procedural Outcomes (including but not limited to):
  - Sedation type
  - Procedure time: time to cecum and withdrawal time including additional time necessary to perform Pure-Vu EVS, in cases where Pure-Vu is utilized.
  - Intraprocedural tools
4. Cecum Intubation Rate
5. Compliance to published interval guidelines for surveillance or repeat screening  
(Prescribed intervals per USMSTF)

## 18) Tertiary Endpoints

- Clinician Satisfaction: Each clinician will complete a questionnaire for each completed Pure-Vu EVS procedure.
- Economic Impact: An assessment of the economic impact will be performed as part of the overall study analysis. Impact will be calculated by utilizing both data generated as part of the study (such as polyp demographics, insurance type, and colonoscopy indication/type) and data published on the costs associated with outpatient colonoscopies and subsequent findings.

## 19) Primary Safety Endpoint

A comparison of SAE rates between Pure-Vu subjects and the published serious complication rate of standard colonoscopy procedures (2.8%).

[figure not shown]
Document Title: Colonoscopy: Demonstrating Effective Salvage of Inadequate Colonoscopies Utilizing the Pure-Vu EVS System	Outpatient	Document No. CL00052	Amendment 2.0	Page 23 of 46
---	------------	--------------------------------	-------------------------	---------------

## **20) Study Design**

This study is a multi-center prospective, consecutive series, pragmatic clinical trial, which reflects real world practices in the outpatient setting. Patients are to be enrolled in a consecutive series manner, be indicated for outpatient colonoscopy and must have attempted or completed bowel preparation regimen. Academic institutions, private practice, outpatient centers and ambulatory surgical centers will be approached for participation in this study.

Below is the diagram of the study design and patient flow.

Document Title: Outpatient Colonoscopy: Demonstrating Effective Salvage of Inadequate Colonoscopies Utilizing the Pure-Vu EVS System	Document No. CL00052	Amendment 2.0	Page 24 of 46
---	-----------------------------	----------------------	---------------

## 21) Selection and Enrollment

A patient may be introduced to the study at the GI office when an outpatient colonoscopy is indicated. Once it's determined that the patient is interested in participation and eligible for participation, he or

Document Title: Colonoscopy: Demonstrating Effective Salvage of Inadequate Colonoscopies Utilizing the Pure-Vu EVS System	Outpatient	Document No. CL00052	Amendment 2.0	Page 25 of 46
---	------------	--------------------------------	-------------------------	---------------

she will be consented for the study. After conducting the consent process, obtaining informed consent, and answering questions, the subject will sign the sites' designated IRB approved informed consent form (ICF). This study also allows for an electronic consenting process. Enrollment of approximately 1,067 subjects is planned to achieve 115 patients with inadequate bowel prep.

Subjects' enrollment in the study will begin on the day of procedure and will last approximately 15 days, including the procedure day, and one follow up call during the follow up period (within 14 days after the procedure). Safety assessments will begin at the time of enrollment.

## **22) Inclusion and Exclusion Criteria**

### **Inclusion Criteria**

1. Eligible adults aged between 40-80
2. Elective outpatient colonoscopy by participating gastroenterologist

### **Exclusion Criteria**

1. Not competent to consent
2. Known or suspected bleeding disorders such as, but not limited to hemophilia and von Willebrand disease
3. History of colonic resection
4. Prior incomplete colonoscopy due to patient anatomy
5. Diverticulitis
6. Active inflammatory bowel disease (Crohn's, Ulcerative Colitis, or Indeterminate)
7. Known or suspected colon stricture/fistula
8. Hereditary Colorectal Cancer Syndrome
9. Subject is pregnant or suspected pregnant

## **23) Withdrawal and Screen Failures**

Subjects may withdraw from the study at their own request or at the request of their legally acceptable representative. The investigator may withdraw a subject from the study at any time for the following reasons:

- Severe side effects clearly related to the study device.

Document Title: Colonoscopy: Demonstrating Effective Salvage of Inadequate Colonoscopies Utilizing the Pure-Vu EVS System	Outpatient	Document No. CL00052	Amendment 2.0	Page 26 of 46
---	------------	--------------------------------	-------------------------	---------------

- Presence or appearance of exclusion criteria.
- Appearance of accompanying diseases rendering further participation in the study impossible.
- A significant protocol violation, as determined either by the sponsor or the investigator
- Subject noncompliant with study procedures

The sponsor must be informed in each withdrawal case. For screen failures, and those satisfying inclusion/exclusion criteria but choosing not to participate in this study, Subject details will be documented in the screen failure log. Subjects who have screen failed will be allowed to re-screen within 120 days of the initial screened date.

## **24) Selection of Investigators and Training**

Board-certified gastroenterologists in accordance with US and hospital guidelines will be considered for participation as investigators in this study. Physicians in training (residents, fellows) and physician assistants may assist the Study Investigator in any aspect of the procedure as per standard practices at his/her institution but will not participate in performing the colonoscopy.

Each Investigator participating in the clinical trial and the associated clinical study staff will receive training on the clinical protocol. This includes training on AE reporting, electronic case report form (eCRF) completion, and Good Clinical Practice (GCP), as well as the study device and system (including procedural use, device characteristics, shelf life and storage requirements, warnings, and precautions), if applicable.

## **25) Study Procedures**

### **26) Screening and Informed Consent**

Once the patient is indicated for an outpatient colonoscopy, he or she will be approached to review the study and obtain consent on the informed consent form (ICF) prior to any study procedures. The purpose of the study and the benefits and risks of the procedures will be explained to the subject and the consent process will be documented accordingly in the medical records. Subjects who agree to study participation must sign an IRB-approved ICF. Subjects will be informed that their participation in this study is voluntary and they may refuse to participate or discontinue from

Document Title: Colonoscopy: Demonstrating Effective Salvage of Inadequate Colonoscopies Utilizing the Pure-Vu EVS System	Outpatient	Document No. CL00052	Amendment 2.0	Page 27 of 46
---	------------	--------------------------------	-------------------------	---------------

the study at any time. Subjects will be given the opportunity to ask the investigator questions so that they are informed about the research. A copy of the signed informed consent must be provided to the subject and the informed consent process will be documented in source documents. This study also allows for an electronic consenting process.

If new information becomes available that may affect a subject's decision to continue to take part in the study, this information will be discussed with the subject by the investigator.

Screened subjects will be documented in the screening log until the subject presents for the day of procedure in which at that time the subject will receive a subject number.

## **27) Day of Procedure (D0)**

On the day of elective outpatient colonoscopy, the subject's eligibility to participate will be assessed again and if still eligible for the study, the subject will be assigned a study subject number in the format of 2-digit Site Number and 3-digit Subject Number (i.e. 01-001, 02-002).

## **28) Pre-Procedure**

If the subject is eligible to continue within the study, the following information will be collected:

- Demographics (age, gender and race)
- BMI
- Relevant medical and surgical history
- Colonoscope type
- Indication for colonoscopy
- Bowel preparation prescription details (type, dose, administration schedule, and diet)
- Bowel preparation consumption details
- Pre-procedure stool clarity grade
- Relevant medications

## **29) Colonoscopy Procedure**

The insertion during the colonoscopy procedure will be performed by the clinical study investigator(s), experienced in GI endoscopy according to the local standard of care. The type of

Document Title: Colonoscopy: Demonstrating Effective Salvage of Inadequate Colonoscopies Utilizing the Pure-Vu EVS System	Outpatient	Document No. CL00052	Amendment 2.0	Page 28 of 46
---	------------	--------------------------------	-------------------------	---------------

sedation will not be dictated by the study but will be documented. The colonoscope will be prepared and the procedure will proceed per the standard of care.

During the procedure, the study endoscopist will be requested to document BBPS for each colon segment. Once the endoscopist notices an inadequate segment, the endoscopist should attempt to cleanse per his/her standard of care practices with the goal to achieve a BBPS of 2 or higher for that segment. This should be repeated for each colonic segment. If the study definition of inadequate is met in any segment, even after SOC cleansing, the endoscopist is required to take pictures of all accessed segment(s) including the inadequate segment(s). The endoscopist will withdraw the colonoscope and all procedural outcomes and findings should be documented. Then the Pure-Vu Oversleeve will be placed onto the colonoscope, and the procedure will be performed utilizing the Pure-Vu System for cleansing. Photo-documentation of each segment will be required to show BBPS after Pure-Vu use. Once the procedure has been completed with Pure-Vu, procedural outcomes (inclusive of final adequacy determination after Pure-Vu use and findings will be documented again.

If during the standard of care colonoscopy, the patient cannot proceed onto Pure-Vu and/or will be deemed an incomplete colonoscopy due to any reason other than inadequate prep, that subject will be withdrawn from the study. Such an instance might occur when a mass or stricture is found, or when an active inflammatory condition is detected but is it ultimately up to the Principal or Sub-Investigator to make the determination during the procedure.

### **30) Post Procedure Follow Up**

As part of the routine post-examination follow up, subjects will be transferred to the recovery room for observation per clinical site's colonoscopy protocol and will continue his/her medical flow as per the standard of care. Follow-up call will be conducted within 14 business days after the procedure to verify that there has been no change in their clinical status. If a clinical status change has occurred (ie. New onset of an AE or worsening condition after day of procedure), then the adverse event should be documented and followed until event resolution or until site is closed by the Sponsor. If no change has occurred, the subject can then be exited from the study.

Document Title: Colonoscopy: Demonstrating Effective Salvage of Inadequate Colonoscopies Utilizing the Pure-Vu EVS System	Outpatient	Document No. CL00052	Amendment 2.0	Page 29 of 46
---	------------	--------------------------------	-------------------------	---------------

In the event a subject does not answer the initial follow-up call, there must be at least two additional, documented attempts to contact the subject within the 14 business day follow up timeframe. If after the additional calls a subject does not answer, they will then be considered lost to follow up.

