## 1) Protocol Synopsis

Study Summary	
Study Purpose	
The aim of this study is to demonstrate that the use of the Pure-Vu EVS System can salvage inadequately prepared optical colonoscopies (OCs) to adequate OCs.
 
Inadequate OCs defined as such if any of the following are met:
 

▪ Boston Bowel Preparation Score (BBPS) < 6 (Adequacy is defined as BBPS of 2 or greater in each segment)

▪ Inability to identify > 5mm polyps

Primary Objective	The primary objective of this study is to demonstrate the reduction of inadequate colonoscopies when Pure-Vu EVS System is used to salvage inadequately prepped colons as defined by the multi-society guidelines (USMSTF).
Secondary Objective	The secondary objective of this study is to assess the impact of the Pure-Vu System on patient outcomes.
Study Procedures	
Protocol Number	CL00052
Protocol Title	Outpatient Colonoscopy: Demonstrating Effective Salvage of Inadequate Colonoscopies Utilizing the Pure-Vu EVS System
Study Sponsor	Motus GI Medical Technologies LTD. [name]

Document Title: Colonoscopy: Demonstrating Effective Salvage of Inadequate Colonoscopies Utilizing the Pure-Vu EVS System	Outpatient	Document No. CL00052	Amendment 2.0	Page 8 of 46
---	------------	--------------------------------	-------------------------	--------------

	[name]
Study Type	Multicenter, Prospective, Consecutive Series, Pragmatic Clinical Trial
Study Device	Pure-Vu EVS System
Study Phase	Post-market
510 (k) Number	K220007 Class II
Study Location	United States
Study Duration	Study period will last approximately 12 months
Planned Follow-Up	Follow-up call will be conducted within 14 business days after the procedure
Subject Population	Patients who are eligible and are scheduled for an outpatient colonoscopy procedure

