## 75) Appendices

### Appendix A: Study Design and Schedule of Assessment

Document Title: Colonoscopy: Demonstrating Effective Salvage of Inadequate Colonoscopies Utilizing the Pure-Vu EVS System	Outpatient	Document No. CL00052	Amendment 2.0	Page 44 of 46
---	------------	--------------------------------	-------------------------	---------------

[figure not shown]
Assessment	Screening /Pre-Procedure (Up to-120 days)	Day of Procedure a (Day 0)	Follow Up (1-14 days post procedure)
Informed Consent and Demographic details	X	X	
Inclusion/Exclusion Criteria	X	X	
Concomitant Medications	X	X	
Medical & Surgical History	X	X	
Body Mass Index		X	
Bowel Preparation Regimen b And Clarity Assessment		X	
Colonoscopy Procedure		X	
Adverse Events Reporting		X	X c
Clinician Satisfaction (only for study device procedures)		X	

aIn the event that patients are screened and enrolled on the same day, all activities must be completed prior to subject entry into the endoscopy suite

bBowel Preparation Regimen information will be collected. Subject must have attempted and or completed bowel preparation to be eligible for study continuation

cPost procedure follow up call will be conducted to ensure reporting of any potential adverse events from the day of procedure

Document Title: Colonoscopy: Demonstrating Effective Salvage of Inadequate Colonoscopies Utilizing the Pure-Vu EVS System	Outpatient	Document No. CL00052	Amendment 2.0	Page 45 of 46
---	------------	--------------------------------	-------------------------	---------------

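### The follow-up call window is given in both business days and calendar days, and exit after any uneventful call lets the period of active SAE detection differ between subjects

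*Protocol*

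**What the plan says.** The length of the call window appears in four places.

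- Synopsis, planned follow-up: "Follow-up call will be conducted within 14 business days after the procedure".
- Section 30: "Follow-up call will be conducted within 14 business days after the procedure to verify that there has been no change in their clinical status". On unanswered calls the same section adds "there must be at least two additional, documented attempts to contact the subject within the 14 business day follow up timeframe", after which the subject counts as lost to follow-up.
- Section 21: "one follow up call during the follow up period (within 14 days after the procedure". The same sentence says that enrollment "will last approximately 15 days, including the procedure day".
- Appendix A, schedule column: "Follow Up (1-14 days post procedure". Adverse event reporting is marked in this column, with a footnote: "Post procedure follow up call will be conducted to ensure reporting of any potential adverse events from the day of procedure".

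On the end of observation, section 30 says: "If no change has occurred, the subject can then be exited from the study". An event found at the call is followed until it resolves or the site closes. Section 54 monitors AEs until the subject completes the study, and longer only for events judged device-related. Section 19 makes the primary safety endpoint a comparison of the SAE rate in Pure-Vu subjects with a literature figure of 2.8%. Section 34 defines the safety population as everyone who presents for the procedure and is enrolled, and uses it for all safety analyses.

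**The concern.** There are two separate problems.

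First, sites and monitors have two rules for the latest acceptable call. A subject first reached on day 17 is in window under section 30 and out of window under section 21 and Appendix A. Whether that is a deviation depends on which page is read.

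Second, whichever unit is meant, the date of an uneventful call can decide how long a subject is actively observed. SAEs are counted against a fixed percentage, and a cumulative percentage depends on how long events are sought. If one site calls on day 2 and another on day 14, the same true risk gives different chances of detection. Because call timing and exit govern conduct, a statistical analysis plan cannot repair this: events that were never sought cannot be recovered in analysis.

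**Working it through.** **Reproducing the stated participation.** Section 21 gives about 15 days including the procedure day. With calendar days, 1 procedure day + 14 days = 15. The figure reproduces, so the plain days of section 21 cannot be shorthand for business days.

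**Converting 14 business days.** Fourteen weekdays are counted forward from each procedure day, with no holidays.

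| Procedure day | Last calendar day of window | Excess over day 14 | Participation including day 0 |
|---|---|---|---|
| Monday | 18 | 4 days (4/14 = 29%) | 18 + 1 = 19 |
| Tuesday to Friday | 20 | 6 days (6/14 = 43%) | 20 + 1 = 21 |

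One holiday inside the window moves the limit to day 21 for every procedure day in the case checked. Against the stated 15 days, 19 and 21 are overruns of 4/15 = 27% and 6/15 = 40%, more than an approximate figure comfortably covers.

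**Where the texts disagree.**

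| First successful contact | Synopsis and section 30 | Section 21 and Appendix A |
|---|---|---|
| Day 1 to 14 | in window | in window |
| Day 15 to 18 or 20 | in window | out of window |
| Later (no holidays) | out of window | out of window |

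**Length of active SAE detection.**

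1. Start: enrollment on the procedure day (section 21).
2. Earliest call: day 1, the only lower limit stated anywhere (Appendix A).
3. Effect of an uneventful call: exit is permitted (section 30).
4. Effect of exit: AE monitoring stops at study completion (section 54).
5. Latest call: day 14 (section 21 and Appendix A), or day 18 to 20 (synopsis and section 30).

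Under Appendix A alone, the permitted span is 1 to 14 days. Section 30 gives no lower limit of its own. With its upper limit and the Appendix A lower limit, the span is 1 to 18 or 20 days.

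**What remains after exit.** The hospitalization criterion in section 44 reaches 24 hours past exit. Section 55 requires reporting of events that the investigator learns of. The first is short and itself tied to the exit date; the second is passive. Follow-up to resolution under section 30 concerns events already found and does not extend the search for new ones.

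**The case against.** The strongest reply is that the protocol does imply a common period. Section 21 says participation lasts about 15 days, and Appendix A marks AE reporting across days 1 to 14. This stands in part. A reader might infer that the protocol sets no observation period at all, and that would go too far: there is a nominal one. But the exit wording in section 30 and the monitoring end in section 54 allow it to be cut short, and no text says that SAE collection continues after an early exit.

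A reader might also infer that the windows cannot both be met. They can: both are upper limits, and a call by day 14 satisfies all four places. Nor does the protocol hold two conflicting lost-to-follow-up rules. Only section 30 has such a rule, and it carries its own 14-business-day window.

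It can fairly be said that a single call within a stated limit is a reasonable choice for a pragmatic post-market study, that day-1 exit is nowhere described as usual, and that section 41 plans descriptive safety summaries. These points limit the weight of the concern. They do not remove the contradiction, or the dependence of SAE detection on the call date.

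Finally, one might spread a 2.8% risk evenly over the window and project how many events early exits would miss. That needs an assumed event timing and an assumed distribution of exit dates. The protocol gives neither, so such a projection should carry no weight.

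**Conclusion.** The contradiction is literal and lies in current text. It amounts to 4 to 6 calendar days before holidays and affects only contacts after day 14.

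The second problem holds in a limited form: a nominal participation of about 15 days is stated, but exit is permitted from day 1 after an uneventful call, so active SAE detection can be shorter for some subjects than for others. The effect on the observed SAE rate can only be downward. Its size cannot be derived, because the protocol gives neither the timing of SAEs nor the expected timing of calls. It also states no decision rule at 2.8% and no observation period behind that figure. It would therefore be wrong to conclude that the safety comparison will reach a different answer, or that a particular window matches the benchmark.

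The primary efficacy endpoint is determined on the day of the procedure, so it and the sample size are untouched. The calendar figures assume a Monday-to-Friday working week. The point should be corrected, and the correction is inexpensive.

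**What to change.** 1. Reconcile the synopsis, section 21, section 30 and Appendix A to one window in one unit. Align the participation length in section 21 and the contact-attempt window in section 30 with it. The choice of window is the sponsor's. For planning, 14 calendar days contain 10 weekdays for the call and its repeat attempts, against 14 in the business-day wording.
2. State one common SAE ascertainment period for the whole safety population of section 34, not only for Pure-Vu subjects, so that follow-up does not differ within the analysis set. The length is left to the sponsor.
3. Align the exit wording in section 30 and the monitoring end in section 54 so that the exit contact falls at or after the end of that period, with room for the repeat attempts. Earlier calls may still be made but should not end SAE collection.

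The cost is wording changes and a call-timing instruction to sites, with no extra visits. Exit calls come later for some subjects, and anyone called early needs a second contact where section 21 now plans one. Loss to follow-up may rise slightly.
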